8 [contact], Email: [contact]

9

10

11

12

13

14

15

16

17

18

19

20

21

22

23

24

25

26

27

28

29

30

31

32

1 **ABSTRACT**

2 *Introduction:* Peripheral artery disease (PAD) is the third most prevalent cardiovascular disease
3 worldwide, with smoking and diabetes being the strongest risk factors. The most prominent symptom
4 is leg pain while walking, known as intermittent claudication. To improve mobility, first line treatment
5 for intermittent claudication are supervised exercise programs, but these remain largely unavailable and
6 economically impractical, which has led to the development of structured home-based exercise
7 programs. This trial aims to determine the effectiveness and cost advantage of TeGeCoach, a 12-month
8 long home-based exercise program, compared with usual care of PAD. It is hypothesized that TeGeCoach
9 improves walking impairment and lowers the need of health care resources that are spent on patients
10 with peripheral artery disease. *Methods and analysis:* The investigators conduct a prospective,
11 pragmatic randomized controlled clinical trial in a health insurance setting. 1760 patients diagnosed with
12 peripheral artery disease at Fontaine stage II are randomly assigned to either TeGeCoach or Care-as-
13 usual. TeGeCoach consists of telemonitored intermittent walking exercise with medical supervision by
14 a physician and telephone health coaching. Participants allocated to the usual care group receive
15 information leaflets and can access supervised exercise programs, physical therapy and a variety of
16 programs for promoting a healthy lifestyle. The primary outcome is patient reported walking ability
17 based on the Walking Impairment Questionnaire. Secondary outcome measures include quality of life,
18 health literacy and health behavior. Claims data is used to collect total health care costs, healthcare
19 resource use and (severe) adverse events. Outcomes are measured at baseline, 12 and 24 months. *Ethics*
20 *and dissemination:* Ethical approval has been obtained from the Medical Association Hamburg. Findings
21 are disseminated through peer-reviewed journals, reports to the funding body, conference
22 presentations and media press releases. Data from this trial are made available to the public and
23 researchers upon reasonable request.

24 *Trial registration:* NCT03496948 (www.clinicaltrials.gov)

25
26
27
28
29
30
31

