Study type	Interventional Allocation: randomized Intervention model: parallel assignment masking: analysis blinding Primary purpose: Prevention
Date of first enrolment	April 2018
Target sample size	1760
Recruitment status	Completed
Primary outcome(s)	PROM: Walking impairment Time points: baseline, 12 and 24 months
Key secondary outcomes	PROMs: Generic health-related quality of life, PAD-specific quality of life, depression, generalized anxiety disorder, alcohol use, nicotine dependence, health literacy, patient activation Claims data: Total health care costs, healthcare resource use, (severe) adverse events Time points: baseline, 12 and 24 months

1

2 Patient and public involvement statement

3 This research was planned without patient involvement. Patients were not invited to comment on
4 the study design and were not consulted to develop patient relevant outcomes. Patients were not
5 invited to contribute to the writing or editing of this document for readability or accuracy.

1
2
3
4
5
6
7
8
9
10
11
12
13
14
15
16
17
18
19
20
21
22
23
24
25
26
27
28
29
30
31
32
33
34
35

Participants

Participants have to meet the following criteria: registered with one of the participating statutory health insurance funds (*KKH Kaufmännische Krankenkasse*, *TK Techniker Krankenkasse*, *mhplus Krankenkasse*); aged between 35 and 80; German-speaking; access to a telephone (landline or mobile); and a primary or secondary diagnosis of PAD at Fontaine stage IIa (> 200 m, Fontaine stage IIa) or IIb (< 200 m, Fontaine stage IIb) within the last 36 months (corresponding ICD-10-GM-codes: I70.21, I70.22, I73.9). Participants should have no primary or secondary diagnosis of PAD at Fontaine stage I (asymptomatic) within the last 12 months, and no diagnosis of Fontaine stage III (ischemic rest pain) or IV (ulcer, gangrene) within the last 36 months to increase diagnostic accuracy (corresponding ICD-10-GM codes: I70.23, I70.24, I73.25).

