 12 ⁸²⁻⁸⁴; nicotine dependence (FTND) ⁸⁵; health literacy (HLQ) ^{86 87}; patient activation (PAM-13
 13 questionnaire) ^{88 89}
- 14 - *Claims data: Total health care costs, i.e. inpatient hospital care costs; outpatient (ambulatory)*
 15 *services and primary care costs, costs for drugs and other medical supplies, sick pay costs;*
 16 *healthcare resource use, i.e. time period until hospitalization, probability of hospitalization,*
 17 *number and duration of inpatient hospitalization, outpatient medical treatment, drug dose*
 18 *(defined daily dose, DDD); (severe) adverse events, i.e. death, amputation, and*
 19 *revascularization (see supplementary file)*

20

21 *Additional outcomes (intervention arm only)*

- 22 - *PROM: Patient satisfaction (ZAPA questionnaire)* ⁹⁰
- 23 - *Activity tracker data: Exercise adherence, e.g. number of alerts and corresponding phone calls*
 24 *made when step frequency or the duration of exercise sessions fall below an individual*
 25 *threshold range; amount of steps/net walking time (>50 steps/minute) per day/week*

26

27

28 **Table 2.** Participant timeline: Time schedule of enrolment (eligibility screen, informed consent, pseudonymization and
 29 allocation), study arms (TeGeCoach or CAU) and measurements (questionnaires and claims data).

	Study period			
	Enrollment	Allocation	Postallocation	
Time point *1	-t1	t0	t1	t2
Enrollment				
Eligibility screening (claims data)	x			
Informed consent	x			
Pseudonymization		x		
Allocation		x		
Study arms				
TeGeCoach (intervention)		◆	◆	◆
CAU (control)		---	---	▶
Measurements				

Intervention and control arm				
PROMs (questionnaires) *2		X	x	x
Cost and medical outcomes (claims data) *3		◆	◆	◆
Intervention arm only				
ZAPA questionnaire			x	
Walking exercise parameters (activity tracker data) *4		◆	◆	

- 1
- 2 *1 -t1: ~1 month before patient in, t0: baseline; t1: 12 month follow-up t2: 24 month follow-up
- 3 *2 WIQ, EQ5D-5L, SF-12, VascuQoL-25, PHQ-9, GHD-7, AUDIT-C, FTND, HLQ, PAM-13
- 4 *3 Health care costs, healthcare resource use, (severe) adverse events
- 5 *4 Exercise adherence, amount of steps/net walking time (>50 steps/minute) per day/week

6

7 **Sample size**

8 To find a ‘meaningful’ effect that is clinically relevant, practicable and economically feasible, the

9 sample size is calculated based on the distribution-based minimal clinically relevant difference (MCID)

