31 to take correlation between the observations into account, models are adjusted for participant and
32 health coaching center characteristics. For claims data, changes over time between groups are
33 compared between study arms using random-effects regression models (difference-in-differences
34 method) after eliminating differences in observable baseline characteristics between groups with the
35 use of entropy balancing⁹⁷. Entropy balancing allows a better balancing compared to conventional

1 processes such as propensity matching. Tests of treatment effects are conducted at a two-sided
2 significance level of 0.05. In order to check the robustness of the results, subgroup analyses are
3 performed to determine the influence of baseline characteristics (e.g. degree of walking impairment),
4 health insurance fund (i.e. *KKH Kaufmännische Krankenkasse*, *TK Techniker Krankenkasse*, *mhplus*
5 *Krankenkasse*) and type of analysis (i.e. intention-to-treat and per-protocol).

6

7 **Data monitoring and harms**

8 This trial is not monitored by a data monitoring committee, and no interim analyses are performed
9 as TeGeCoach is a low risk, non-invasive intervention with no identifiable risks. Over the course of the
10 intervention, participants allocated to TeGeCoach are medically monitored by their treating physician
11 while having regular access to the usual care of PAD. The risks from the use of wearable activity trackers
12 is low; all devices have been certified and conform to health, safety, and environmental protection
13 standards for products sold within the European Union (CE certificate).

14

15 **Ethics and Dissemination**

16 The study protocol, the informed consent forms and all other documents that are handed out to the
17 participants have been reviewed and approved by the ethical review bodies (Medical Association
18 Hamburg; reference number: PV5708). The ethics committee will be informed in case of any
19 amendments made to the study protocol or informed consent forms.

20 Findings are disseminated widely through peer-reviewed manuscripts published in scientific journals,
21 reports to the funding body, international conference presentations and media press releases.
22 Furthermore, the study team realizes the value of open science and feels committed to information
23 exchange through data being accessible to the research community. Therefore, in an attempt to tackle

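### Difference-in-differences is named for all claims data, but a pre/post change is undefined for time until hospitalisation in patients never admitted, and for costs it is never more precise than baseline-adjusted regression

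*Combined protocol and SAP*

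**What the plan says.** The Statistical analysis section gives one method for claims data. Changes over time are "compared between study arms using random-effects regression models (difference-in-differences" "method) after eliminating differences in observable baseline characteristics between groups with the" use of entropy balancing. Tests are two-sided at 0.05. The section does not list the balancing variables, the length of the pre-period, the link function, a censoring rule, the handling of death, or how the standard error (SE) allows for estimated weights.

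The claims outcomes are listed under Outcome Measures, Secondary Outcomes. Besides costs, they include "healthcare resource use, i.e. time period until hospitalization, probability of hospitalization", the number and duration of admissions, and death, amputation and revascularisation. The list ends by citing a supplementary file, which was not among the documents seen. Table 1 gives the set as "Claims data: Total health care costs, healthcare resource use, (severe) adverse events", with time points baseline, 12 and 24 months. Participants are randomised 1:1, stratified by coaching centre.

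The outcomes are secondary, but they carry one of the trial's two hypotheses: the Abstract expects that TeGeCoach "improves walking impairment and lowers the need of health care resources that are spent on patients" with the disease.

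**The concern.** Difference-in-differences (DiD) compares a before-to-after change between arms. Costs have a before and an after value in every patient alive and insured. Time until hospitalisation does not: follow-up stops at 24 months, some patients die first, and anyone not admitted has no observed time. A change then exists only for patients admitted in both periods, unless the others are given a time or the model works on the hazard. The plan does not say which. Some of these choices select patients on an event after randomisation; others can lose much of the power to see a real reduction.

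For costs the issue is milder. In a randomised trial the pre-period difference is zero in expectation, so subtracting it removes no bias. It can add noise compared with adjusting for the baseline value.

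**Working it through.** **The plan's own figure.** The documents give no power or precision for claims outcomes. The stated sample size is for the questionnaire outcome and reproduces: f = 0.15 is d = 0.30, 176 per arm gives 80.1% power, and 176/0.20 = 880 per arm. It does not bear on this point, except that 880 per arm is used below.

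**Time until hospitalisation: assumptions.** All are mine: hazard ratio 0.8, control 24-month risk p = 30/40/50%, death 3% per year, 24-month pre-period, exponential times. Hazards per month are λc = −ln(1−p)/24, λt = 0.8λc and λd = −ln(0.97)/12 = 0.00254.

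*Admissions.* Expected number per arm = 880·λ/(λ+λd)·[1−exp(−24(λ+λd))]. At p = 30%, λc = 0.01486, giving about 257 + 212 = 469 in total; at 40% and 50%, 629 and 793. So at 30%, 1,760 − 469 = 1,291 patients have no observed follow-up time.

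*Cox.* Power = Φ(|ln 0.8|·√(E/4) − 1.96). At 30%: 0.2231 × √(469/4) − 1.96 = 0.456, or 68%. At 40% and 50%: 80% and 88% (simulated: 67/80/88%).

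*Observed times only.* With a = λ+λd, mean time among the admitted = 1/a − 24e^(−24a)/(1−e^(−24a)). Control versus treated: 11.17 vs 11.31 months at 30%, 10.86 vs 11.06 at 40%, 10.51 vs 10.78 at 50%. A 20% hazard reduction almost disappears. Only 141/252/396 patients are expected to have both times. Simulated power is 6/5/6% with complete pairs and 5/5/7% with a random-intercept model on every observed time.

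*Log-hazard DiD, no balancing.* SE = √(1/Ec + 1/Et + 2/(880p)). At 30%: √(1/257 + 1/212 + 2/264) = 0.127, and Φ(0.2231/0.127 − 1.96) = 42%. At 40% and 50%: 53% and 62%.

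*With entropy weights on pre-period hospitalisation.* Simulated power (%), control risk 30/40/50%, no frailty:

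| Version | Not balanced | Balanced, SE treats weights as fixed | Balanced, true sampling SD |
|---|---|---|---|
| Non-admitted set to end of follow-up | 33/40/49 | 23/40/50 | 57/72/81 |
| Log-hazard DiD | 43/53/62 | 40/55/66 | 68/80/89 |
| Unadjusted post-period comparison | 67/81/89 | – | – |

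These figures carry simulation error of a few points. With gamma frailty of variance 1 and the true SD, risks 30/40/50/60% give 58/64/74/78% for log-hazard DiD and 54/61/73/79% for assigned times, against 53/63/69/70% unadjusted.

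**Costs.** Let s0 and s1 be the baseline and follow-up SDs and ρ their correlation. The per-arm variance factor is s1² + s0² − 2ρs0s1 for DiD and s1²(1−ρ²) for baseline adjustment. The difference is (s0 − ρs1)², which is never negative. Let k = s1/s0, and let r be the correlation of a balanced covariate with baseline cost (acting on follow-up cost only through it). Then

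SE ratio = √{[1 + k² − 2ρk − r²(kρ−1)²] / [k²(1−ρ²)]}.

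| k | r | ρ = 0.2 | 0.3 | 0.5 | 0.7 |
|---|---|---|---|---|---|
| 0.8 | 0 | 1.466 | 1.411 | 1.323 | 1.262 |
| 1 | 0 | 1.291 | 1.240 | 1.155 | 1.085 |
| 1.5 | 0 | 1.108 | 1.071 | 1.018 | 1.001 |
| 0.8 | 0.5 | 1.364 | 1.321 | 1.250 | 1.202 |
| any | 1 | 1.000 | 1.000 | 1.000 | 1.000 |

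Skewed costs behave alike. In lognormal simulations with parameter 0.3/0.5/0.7 on the log scale, the variance ratio was 1.67/1.47/1.27 without balancing and 1.01-1.03 with baseline cost balanced. When baseline cost is balanced, an SE that treats the weights as fixed is 1.26/1.26/1.18/1.08 times the true SD at ρ = 0.2/0.3/0.5/0.7 (normal data, k = 1; coverage 98.5/98.6/97.8/96.6%).

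**The case against.** The strongest reply is that the plan specifies DiD after entropy balancing, so power figures without weights describe a different procedure. That stands. A reader might infer that DiD always loses power for time until hospitalisation; the documents do not support this, because the log-hazard version recovers full power when prior hospitalisation is balanced and the SE reflects weight estimation. The loss is conditional on two things the plan leaves open.

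Second, random-effects regression is a family of models and does not exclude a hazard model. This is fair, but no time-to-event model or censoring rule is named, and the stated target is a change over time. A reader might also infer that the plan will discard patients never admitted. It does not say so, and its intention-to-treat commitment points the other way. The 5% figure shows what one unexcluded reading would do, not what is planned.

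Third, baseline cost is an obvious balancing variable. If it is used, the true precision loss for costs disappears and only a possibly conservative SE remains. To read the cost point as bias would be wrong.

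Fourth, death has no baseline value to difference, which might look like a further fault. It is not one: a linear DiD then reduces to the follow-up risk difference, and the plan names no link under which it would fail. None is claimed for the other binary and count outcomes either.

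Finally, the supplementary file may say more. It is cited beside the outcome list, not in the analysis section.

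**Conclusion.** The point holds in a limited form. For time until hospitalisation, the named estimator does not define a value for patients never admitted. Depending on how the gap is filled, power runs from about 5% to about that of an ordinary unadjusted comparison; Cox gives about 67/80/88% without needing the gap filled. Setting non-admitted patients to end of follow-up stays below the unadjusted comparison without frailty even in the favourable case, and is about equal with frailty. The problem is power and what is being estimated, not false positives: simulated type I error at a hazard ratio of 1 was 3.9-5.2% for all methods, without the weights.

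For costs, DiD is unbiased, but in large samples never more precise than regression on the baseline value with the same covariates. Intervals are 0-47% wider over ρ = 0.2-0.7 and SD ratio 0.8-1.5 if neither baseline cost nor a correlate is balanced, and no wider in truth if baseline cost is balanced.

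All event rates, the hazard ratio, frailty, correlations and SD ratios are assumptions, with the hazard ratio and death rate held at single values. The walking-impairment analysis and the sample size are unaffected.

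**What to change.** - **Time to first hospitalisation:** use a cause-specific Cox model stratified by coaching centre and pre-period hospitalisation (yes/no), with death as a competing event and cumulative incidence reported by arm. The stratification helps where patients differ in underlying risk: at 60% control risk, frailty variance 1 and a 12-month pre-period, simulated power was 77.4%, against 69.8% for unstratified Cox and 74.3% for unweighted DiD with assigned times.
- **Costs:** regress the follow-up value on arm, baseline-period value, coaching centre and the covariates that would have been balanced, with robust or bootstrap SEs.
- **Entropy-balanced DiD:** keep it as a sensitivity analysis. List the balancing variables, including baseline cost and prior hospitalisation, state the pre-period length, and re-estimate the weights in each bootstrap sample.

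The cost is plan wording and slightly more analysis work, with no new patients. Data collection and management says the funds assemble the claims extract after study completion, so admission and death dates can be specified in that request. Treatment allocation and blinding says group codes are withheld until analytical decisions are complete, so the wording can be settled before then.

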6 prerequisite for receiving the TeGeCoach intervention; participants can elect their preferred physician
7 prior to program start, or are alternatively referred to an already contracted physician by their health
8 coach. To encourage physicians to participate, they enter into an integrated care contract with the
9 respective health insurance fund that provides financial incentives for the delivery of special medical
10 services throughout the intervention.⁶⁷ The enrolment and reimbursement of contracted physicians is
11 coordinated by medicalnetworks (Kassel, Germany), a company that is specialized on the management
12 of integrated care programs (ICPs) within the § 140a volume V of the German Social Security Code (SGB
13 V). If the physician of choice refuses to participate, the participant is referred to a nearby contracted
14 physician that has already entered into the integrated care contract. Once enrolled, the health coach
15 contacts the contracted physician to discuss their tasks during the course of the study. Due to
16 recruitment barriers, it is possible that no suitable physician can be found for the patient by the end of
17 the recruitment phase. For safety reasons, participants for whom no physician can be appointed do not
18 receive TeGeCoach.

19

20 **Treatment allocation and blinding**

21 Participants are allocated in a 1:1 ratio to either the TeGeCoach or CAU group, stratified by health
22 coaching center using a permuted block method within each stratum. In order to prevent selection bias
23 and to eliminate any predictability (allocation concealment), participants are randomly allocated via
24 Sealed Envelope (London, United Kingdom), a secure internet-based randomization service including
25 concealment, stratification and blocking for each health coaching site.

26 Blinding of care providers (health coaches and contracted physicians) and participants is not possible
27 because of obvious differences between the TeGeCoach intervention and CAU. However, as supported
28 by the CONSORT guidelines, blinding of the analysis is achieved by engaging an independent data analyst
29 and by withholding information about how the groups were coded before analytical decisions have been
30 completed.⁶⁸

31

32 **Interventions**

33 *TeGeCoach*

34 TeGeCoach is a 12-month long structured HEP that is designed to inspire healthy habits in patients
35 with PAD based on the transtheoretical model of behavior change. The main strategies used to improve

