4 Claims data are routinely collected for the purpose of billing and contains information on all contacts
5 with the health care system including ICD codes, operations and procedure key (OPS) codes (the German
6 equivalent to the American procedure coding system, PCS), medication prescriptions and amount of sick
7 leaves. After study completion, the health insurance funds assemble and pseudonymize the claims data
8 and send it to the study team (University Medical Center Hamburg-Eppendorf). No individual insurance
9 information can be identified from this data.

10 Activity tracker data are automatically uploaded to the electronic documentation system via SIM card
11 modem (econnect, IEM GmbH) once per day. The statutory health insurance funds share the activity
12 tracker data with the study team in pseudonymized form.

13 All data are stored for a maximum of 10 years, securely locked in cabinets and saved on password-
14 protected computers in areas with restricted access. Personally identifiable information of participants
15 and pseudonymization keys are only accessible to the data coordinators at each health insurance fund.
16 The pseudonymization keys are deleted two years after study completion so that virtually from this point
17 all data is fully anonymized. Regarding dissemination, all publicly available data are fully anonymized
18 and do not disclose identities. Participants have the right to be informed about their data. If a participant
19 decides to withdraw from the trial prematurely, the data already collected may be used, unless revoking
20 their informed consent. Deletion of the data cannot be requested if the data has already been
21 anonymized.

22

23 **Statistical analysis**

24 Analyses are by intention-to-treat in accordance with the CONSORT guidelines, i.e. participants who
25 do not adhere to or withdraw from the prescribed TeGeCoach intervention and for whom no doctor
26 could be appointed (see *recruitment* section) are included in the analyses as randomized. For
27 questionnaire data, changes from baseline to follow-up measurements are compared between study
28 arms using linear mixed models.⁹⁴ Single imputation using the Expected-Maximization algorithm are
29 applied for item-level missing data. Scale-level imputation of missing data is not necessary since this is
30 fully handled by estimating mixed models with full information maximum likelihood (FIML).^{95 96} In order

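### Claims costs in a 1:1 randomised, intention-to-treat trial are analysed by entropy balancing plus difference-in-differences, with balancing variables and standard errors unstated; this can widen cost intervals but does not bias them.

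*Combined protocol and SAP*

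**What the plan says.** Under Treatment allocation and blinding: "Participants are allocated in a 1:1 ratio to either the TeGeCoach or CAU group, stratified by health" coaching centre, in permuted blocks. Under Statistical analysis, patients who do not adhere, who withdraw from the intervention or for whom no physician is found "are included in the analyses as randomized".

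The same section gives claims data a separate method. Changes over time are "compared between study arms using random-effects regression models (difference-in-differences" method), "after eliminating differences in observable baseline characteristics between groups with the" use of entropy balancing. The only reason offered is that "Entropy balancing allows a better balancing compared to conventional" approaches such as propensity matching. The section does not list the balancing variables, say whether pre-randomisation cost is among them, or say how standard errors allow for the weights having been estimated.

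Table 1 lists the claims outcomes as "Total health care costs, healthcare resource use, (severe) adverse events", with baseline as one of the time points. The Introduction makes lower health care costs one of the two parts of the trial's hypothesis.

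**The concern.** Entropy balancing and difference-in-differences are mainly tools for non-randomised comparisons. Here randomisation has already made baseline differences between the arms a matter of chance, and the stated advantage over propensity matching answers a confounding problem that the intention-to-treat comparison does not have.

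What remains is precision. A patient's cost before randomisation is usually informative about later cost, and regression adjustment uses that information at its best weight. Differencing forces the weight to be 1. Balancing on baseline cost can recover the loss in the point estimate, but the reported interval shows the gain only if the standard error allows for the estimated weights. Since the plan settles neither matter, the cost intervals could be wider than the planned data require.

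**Working it through.** **Inputs.** From the documents: 1:1 allocation, 880 per arm, intention to treat, two-sided 5%, and the claims model above. Assumed, because the documents do not give them: rho, the correlation between a patient's pre-randomisation and follow-up cost, and k, the follow-up SD divided by the baseline SD.

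**The plan's own figure.** There is no power or precision figure for costs. The only sample-size figure is for walking impairment, and it reproduces: f = 0.15 is d = 0.30 for two equal groups, 176 per arm gives 80.1% power, and 176/0.20 = 880 per arm. It has no bearing on costs.

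**Step 1: plain differencing against adjustment for baseline cost.** In units of the baseline variance:

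- variance of a change score: k² + 1 − 2·rho·k
- variance after adjustment for baseline: k²(1 − rho²)
- first minus second: (1 − rho·k)², never negative, and zero when rho·k = 1

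The ratio of interval widths is sqrt[(k² + 1 − 2·rho·k) / (k²(1 − rho²))]. For example, k = 1 and rho = 0.5 give sqrt(1/0.75) = 1.155.

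| k | rho 0.2 | rho 0.5 | rho 0.8 |
|---|---|---|---|
| 0.75 | 1.529 | 1.388 | 1.338 |
| 1 | 1.291 | 1.155 | 1.054 |
| 1.25 | 1.173 | 1.058 | 1.000 |
| 1.5 | 1.108 | 1.018 | 1.024 |
| 2 | 1.046 | 1.000 | 1.118 |

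**Step 2: do the random effects help?** No. On complete simulated data (300 per arm), the arm-by-time interaction from a random-intercept model was 0.00459 (SE 0.08336), and the difference in mean change was also 0.00459 (SE 0.08336).

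**Step 3: baseline cost balanced, weights treated as fixed.** Simulation with 880 per arm, 4,000 trials and k = 1, with controls weighted to the TeGeCoach mean baseline cost. Results at rho 0.2 / 0.5 / 0.8:

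- The true SD of the estimate relative to baseline adjustment was 1.00 / 1.00 / 1.00 with normal data and 1.00 / 1.01 / 1.02 with lognormal data. The estimate itself is therefore about as precise.
- The reported SE divided by the true SD was 1.32 / 1.15 / 1.06 (normal) and 1.28 / 1.16 / 1.05 (lognormal).
- Type I error was 1.1 / 2.7 / 3.8% (normal) and 1.2 / 2.2 / 3.7% (lognormal), that is, conservative.

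With fixed weights, the reported SE stays near that of plain differencing whichever variables are balanced: about 1.3 / 1.16 / 1.05 times that of adjustment for baseline cost.

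**Step 4: baseline cost balanced, weights re-estimated in each bootstrap sample** (100 trials, 200 samples each). The SE relative to baseline adjustment was 0.994 / 0.995 / 0.996 (normal) and 1.009 / 1.015 / 1.024 (lognormal). The loss disappears.

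**Step 5: other balancing variables.** A second simulation (880 per arm, 3,000 trials, k = 1) added a covariate that predicts follow-up cost. The true SE relative to adjustment for baseline cost alone, at rho 0.3 / 0.5 / 0.7, was:

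- balancing only that covariate, then differencing: 1.10 / 1.00 / 0.84
- balancing cost and that covariate, then differencing: 0.84 / 0.81 / 0.73
- regression adjustment for both: 0.84 / 0.81 / 0.73

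The comparison is therefore fair only with the same covariates on both sides. On those terms, the planned method matches regression adjustment at best. When the effect of baseline cost on follow-up cost differed by arm (rho 0.5), balancing cost and then differencing had a slightly larger SE, 1.046.

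**The case against.** The strongest reply is that the plan does not propose plain differencing. Baseline costs are a planned measurement, so the characteristics to be balanced may well include them, and the estimate would then be about as precise as an adjusted one. This stands for the point estimate. It does not settle the reported interval, which keeps the width of plain differencing if the weights are treated as fixed (Step 3).

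A second reply is that balancing on other strong predictors can beat adjustment for baseline cost alone. That is correct (Step 5), and it is why any replacement model must carry the same covariates.

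Third, a per-protocol comparison is also planned, patients may revoke consent, and a supplementary file is cited for the claims outcomes. The first gives a reason to balance in the per-protocol analysis, not in the intention-to-treat one. Revoked consent could in principle unbalance the arms, but the plan does not offer it as its reason. The supplementary file is not in the material reviewed; it is cited for the list of claims outcomes, not for the model.

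A reader might infer more than the documents support:

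- That the method biases the cost result or raises false positives. Under randomisation it does neither; simulated type I error was at or below about 5%.
- That the cost intervals will certainly be wider. The plan does not say which variables are balanced or how standard errors are obtained, and the loss is nil when rho·k = 1.
- That cost power is reduced by a known amount. No correlation, SD or target difference for costs is given.

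**Conclusion.** The point holds as one of precision and specification. For the intention-to-treat cost comparison, entropy balancing plus difference-in-differences is never more precise in large samples than regression adjustment for the same baseline covariates including pre-randomisation cost. With fixed weights it reports conservative intervals even when cost is balanced. Under assumed equal SDs, these are about 29%, 15% and 5% wider than under adjustment for pre-randomisation cost at rho 0.2, 0.5 and 0.8. Over the other SD ratios examined, the widening from plain differencing runs from nil to 53%. These sizes rest on assumed rho and k and are illustrative.

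This is a minor-to-moderate improvement to a secondary outcome. It is worth making because lower cost is part of the stated hypothesis and the remedy costs almost nothing.

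**What to change.** Either change is sufficient, for the intention-to-treat analysis of costs and other continuous or count utilisation.

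- **A.** Compare the arms on follow-up values on the mean scale, adjusting for the patient's pre-randomisation value, coaching centre and the same baseline characteristics that would have been balanced, with robust or bootstrap standard errors. Keep entropy-balanced difference-in-differences as a sensitivity analysis. Dropping those other characteristics could lose precision, so they must stay.
- **B.** Keep the planned method, name the balancing variables with pre-randomisation cost among them, and re-estimate the weights in each bootstrap sample.

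The cost is a prespecified covariate list and slightly more analysis work. No new data are needed: baseline claims are already a planned time point, and "After study completion, the health insurance funds assemble and pseudonymize the claims data".
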